As a precursor to a large, definitive randomized clinical trial, this pilot study will examine the components of patient recruitment and retention, assessment of exertional capacity, and program implementation of this intervention with the goal that they will be employed in a larger scale study and possibly to all TAVR programs in the United States. To this end, all components of this study were chosen not only for clinical efficacy, but also for cost effectiveness and ease of implementation into current “real world” TAVR programs.

Primary Efficacy Outcomes

- **Functional exercise capacity – Change in 6 Minute Walk Test (6MWT)**
Measure: Does prehabilitation improve the subject’s functional exercise capacity from first PT assessment to pre-procedure assessment and first PT assessment to one month post-procedure, as measured by the 6MWT?

Secondary Efficacy Outcomes

- **Mobility – Timed Up-and-Go (TUG) test**
Measure: Does prehabilitation improve the subject’s mobility from first PT assessment to pre-procedure assessment and first PT assessment to one month post-procedure, as measured by the TUG test?
- **Balance – Four Square Step Test (FSST)**
Measure: Does prehabilitation improve the subject’s balance from first PT assessment to pre-procedure assessment and first PT assessment to one month post-procedure, as measured by the FSST?
- **Discharge disposition**
Measure: Does prehabilitation make it less likely that a patient will require a higher level of care at discharge than they required prior to admission (for example, arrive from home and discharged to home)?
- **Length of stay in Intensive Care Unit (hours)**
- **Total hospital length of stay (days)**

- **Change in quality of life**
Measure: Does Kansas City Cardiomyopathy Questionnaire score change from first PT assessment to one month post-procedure?
- **30-day readmission**
Measure: Does the subject have a 30-day readmission post-procedure?

Safety Outcomes

- Syncope
- Major adverse cardiac events (MACE)
- Falls and musculoskeletal adverse events
- Adverse events from other complications
- Serious adverse events, including those that require hospitalization

Hypotheses

1. Monitored pre-procedural physical therapy is safe for patients identified as frail who are undergoing transcatheter aortic valve replacement.
2. Monitored pre-procedural physical therapy in patients to undergo transcatheter aortic valve replacement will result in:

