A Data Safety Monitoring Board (DSMB) will monitor all AEs and SAEs to provide safety oversight. DSMB members will not be involved in the study and have no conflict of interest.

Redcap will be the database that will provide data management through a secure, password protected Electronic Data Capture (EDC) system accessible via the Internet. A unique Patient ID will be assigned for each patient enrolled in the study. All pertinent data will be entered by the study site personnel into the electronic Case Report Forms (eCRFs).

Every reasonable effort should be made to complete data entry within 5 business days of data collection. Data review by Quality will occur remotely as well as during on site monitoring. Data discrepancies will be queried and resolved through the EDC system.

The site Principal Investigator or designee must ensure the accuracy and completeness of the recorded data and then provide his/her electronic signature on the appropriate eCRFs. Changes to data previously submitted to the Sponsor will require a new electronic signature to acknowledge/approve the changes.

Risks and risk management

The primary potential physical risks to patients enrolled in this study appear to be adverse cardiac events including dizziness, syncope, angina pectoris, ventricular tachycardia, or sudden cardiac death. Observation studies report exertional dizziness or syncope in patients with severe aortic stenosis suggesting this is a potential risk for patients in this study. Also, ventricular tachycardia has been reported in early studies of patients with severe aortic stenosis undergoing exercise stress tests however this has not been reported in contemporary studies. Other potential physical risks include falling or pain due to exercise.

To mitigate these risks, all potential participants will undergo a complete history and physical examination by a cardiologist prior to enrollment. Any patient determined to be at high risk for adverse clinical event by the cardiologist will be excluded. Also, all participants will undergo standard TAVR non-invasive and invasive testing; this includes: transthoracic echocardiography, transesophageal echocardiography, right and left heart catheterization, and Computer-Assisted Tomography (CAT scan) of the chest, abdomen, and pelvis. Patients with un-revascularized coronary artery disease will not be enrolled in the study.

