Transcatheter Technologies (TCT) national meeting. Also, it is planned that the results will be submitted for publication in a peer –review scientific journal.

Delineation of resources required to conduct the study

The resources required to conduct this study include research coordinators and physical therapists. No special software, equipment, processes, or tests are needed to conduct this study.

ADVERSE EVENTS

Adverse Event

An Adverse Event (AE) is any untoward medical occurrence, unintended injury or untoward clinical signs in patients, users or other persons, related to the study.

Adverse events may be volunteered by patients, elicited by the Investigator or designee, or collected via observation by the Investigator. All AEs will be assessed by the Investigator who will determine whether or not the event is related to the study, and whether or not the event meets serious criteria. If it is determined that an AE has occurred, the investigator should obtain all the information required to complete the AE Form of the CRF. Source documents should be collected for each AE. In addition, patients will be instructed to contact the investigator, and/or study coordinator if any significant adverse events occurs between study visits.

Serious Adverse Event

An Adverse Event is considered serious if the event:

1. Leads to death;
2. Leads to a serious deterioration in the health of the study patient that:
 - Results in life-threatening illness or injury;
 - Results in a permanent impairment of a body structure or a body function;
 - Requires inpatient hospitalization or prolongation of existing hospitalization;
 - Results in medical or surgical intervention to prevent permanent impairment to body structure or a body function;
3. Significant medical event.

References

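### The adverse event definition requires relatedness to the study, while the next paragraph leaves relatedness open; read literally, unrelated events fall outside AE Forms, SAEs and DSMB review

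*Combined protocol and SAP*

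**What the plan says.** All references are to the combined protocol and SAP.

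- **ADVERSE EVENTS, Adverse Event, definition.** The list of qualifying occurrences closes with "untoward clinical signs in patients, users or other persons, related to the study".
- **Same section, next paragraph.** For all AEs the investigator is to "determine whether or not the event is related to the study, and whether or not the event meets serious criteria". Then: "If it is determined that an AE has occurred, the investigator should obtain all the information required to complete the AE Form". Patients are also asked to contact the study team "if any significant adverse events occurs between study visits".
- **Serious Adverse Event.** The definition builds on the AE definition: "An Adverse Event is considered serious if the event" meets one of the listed criteria.
- **Data analysis and Data Monitoring.** "A Data Safety Monitoring Board (DSMB) will monitor all AEs and SAEs to provide safety oversight".
- **Safety Outcomes.** Five items, among them syncope, MACE and "Serious adverse events, including those that require hospitalization". None is limited to related events.
- **Hypotheses, item 1.** "Monitored pre-procedural physical therapy is safe for patients identified as frail who are undergoing transcatheter aortic valve replacement".
- **Visit chart under Research procedures.** Adverse events are marked at the prehabilitation visits and at the pre-operative assessment. A footnote to the pre-operative mark wants both groups assessed before TAVR, so that control-arm events arising without the therapy can be seen. The Pre-operative Assessment list under Subject Schedule names only the three physical tests and the questionnaire, with no AE item.
- **30-day and 1-year Follow-up Assessments.** Health-record monitoring starts at the discharge date and names syncope, MACE, falls, readmission and mortality individually.

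**The concern.** Safety is the first hypothesis of this pilot, and the DSMB's remit is expressed in AEs and SAEs. If relatedness is a condition of being an AE, the investigator's causal judgement decides whether an event enters the record at all, instead of describing an event already recorded. Everyone at the site can see who attends sessions, and the document describes no blinding of the investigator, so that judgement could be made differently in the two arms. The safety outcomes and the chart footnote point to a record of what happened in each arm whatever the cause. The definition, taken at its word, would give something narrower.

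**Working it through.** The document states no AE rate, safety threshold or safety sample size, so there is no figure to reproduce. The check sets the texts side by side.

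1. **Can both sentences govern?** If the definition governs, every AE is related, and determining relatedness for each AE can return only one answer. If the determination is meaningful, some AEs are unrelated, and the closing condition of the definition is wrong. They cannot both stand.

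2. **What follows if the definition governs?**
   - An event judged unrelated is not an AE (definition).
   - The AE Form is triggered only once an AE is determined to have occurred, so no form is required.
   - An SAE is an AE with an added criterion, so the event cannot be an SAE, however severe.
   - The DSMB monitors AEs and SAEs, so the event is outside its stated scope.

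3. **Is there an escape route?** No section says that AEs count irrespective of relationship to the study, and none sends unrelated events to the DSMB by another path.

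4. **Where does it bite?**
   - *Randomisation to TAVR.* Subjects are randomised at the end of the intake visit, and treated subjects then attend 8 to 12 sessions over 3 to 5 weeks. In this window the Prehabilitation list and the chart introduce MACE, syncope, falls and SAEs as kinds of adverse event, so the definition reaches them. Health-record monitoring has not begun. Events between visits rest on patient report and the pre-operative check.
   - *After discharge.* Syncope, MACE, falls, readmission and mortality are named for collection in all subjects, so their capture does not depend on the AE definition. The items for other complications and for SAEs still use the defined terms.

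5. **Can the bias be sized?** Let p_T and p_C be the true event proportions, and k_T and k_C the shares of events kept after the relatedness judgement. Then

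   observed ratio = (p_T / p_C) × (k_T / k_C).

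   If k_T = k_C the ratio is unchanged. If k_C < k_T it is inflated against treatment, and if k_T < k_C it is deflated. The document supplies the arm size (35 per group) and none of these four quantities, so neither size nor sign can be calculated.

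**The case against.** The strongest reply is that the intent is clear. The investigator's task presupposes that an AE may be unrelated, the AE Form and DSMB sentences carry no relatedness filter of their own, and the outcome lists and the chart footnote carry none either. On that view this is one stray phrase against consistent operational text. The phrase might even attach only to users or other persons, which would remove the conflict. The point about intent stands, and it shows which sentence to correct. It does not tell site staff which sentence to follow, and the comma before the phrase makes it more naturally govern the whole list.

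A second reply also has force: being related to the study is not the same as being related to prehabilitation. Controls perform the same study walking and balance tests, so their events can be study-related. The definition therefore does not contradict the chart footnote directly, although it can work against the footnote's purpose.

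A reader might infer several stronger things that the documents do not support:

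- *Unrelated events are not collected at all.* The post-discharge lists say otherwise.
- *Such events can never be re-examined.* Those that reached the health record could be retrieved.
- *Control-arm events would be lost preferentially, creating a false excess in the treatment arm.* A relatedness filter also removes unrelated treatment-arm events, and nothing shows how the judgement would differ by arm.
- *Two chart columns with AE marks for treatment against one for control show biased ascertainment.* The extra column reflects sessions that only treated subjects attend, the chart already marks a pre-operative check in both arms, and the size of any effect is unknown.

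**Conclusion.** The wording conflict is certain: two adjacent paragraphs give incompatible roles to relatedness. The consequence is conditional. It arises if the definition is applied as written, in which case unrelated events drop out of AE Forms, SAE classification and DSMB scope, with the main exposure between randomisation and TAVR. Arm-dependent judgement is possible because no blinding of the investigator is described, but bias of a particular size or direction cannot be claimed. The correction is worth making because the affected record supports the first hypothesis and the DSMB's oversight, and because recording all events keeps a related-only analysis available, whereas the reverse is not assured.

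**What to change.** 1. In the AE definition, keep the kinds of occurrence already listed and replace the closing condition with a statement that they count irrespective of any relationship to the study.
2. Record relatedness as a separate attribute on the AE Form.
3. State that SAEs, and the AEs and SAEs reported to the DSMB by arm, are not limited to related events.
4. Add the AE check to the Pre-operative Assessment list under Subject Schedule, so that it matches the visit chart.

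The cost is wording changes and some more AE forms for events later coded as unrelated, in a trial of 70 subjects. No visit or test is added.
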